The study has been initiated by doctors from the pacemaker implanting centres in Denmark. The study organisation will apply private and public foundations for financial support to cover the study expenses. The Danish Heart Foundation has granted DKK 512.000, Arvid Nilssons Foundation DKK 200.000, The Danish Council for Independent Research DKK 1.800.000, The Danish Pacemaker and ICD Register DKK 600.000, and Karen Elise Jensen's Fund DKK 500.000. The principal investigator is a member of The Danish Heart Foundation and part of their biomedical research committee. The principal investigator has no relation to Arvid Nilssons Foundation, Karen Elise Jensen's Foundation or The Danish Council for Independent Research. Remote monitoring is not general practise in patients with pacemakers. Therefore, we have applied the pacemaker companies for coverage of the expenses for remote monitoring during the study period. The patients receive no compensation for their participation in the study.

26. Feasibility

With an annual number exceeding 1000 of primary pacemaker implantations in patients with SSS in Denmark the study is considered feasible. The organisation of Danish centres performing pacemaker implantations recently finalized the DANPACE trial [2] which has impacted current international guidelines on cardiac pacing (13). The principal investigator has a long-standing experience in

conducting and coordinating single- and multicentre trials within the field of arrhythmia management (14-16).

27. Publication

The study results, positive or negative, will be published in an international journal with the members of the steering committee as co-authors (requires inclusion of at least 25 patients at the centre).

28. Summary

Atrial fibrillation (AF) is observed in 50 % of the patients with sick sinus syndrome (SSS) within the first two years after pacemaker implantation. Studies have indicated that the incidence of AF increase with higher proportion of atrial pacing. The purpose of the DANPACE II trial is to test the hypothesis that reducing the amount of atrial pacing by programming a lower rate of 40 bpm with the rate response function off reduces the incidence of AF compared to conventional pacemaker programming with a lower rate of 60 bpm and activated rate response function in patients with SSS. In a multicentre randomized study 540 patients will be randomized equally between the two study arms over two years with a follow-up period of two years. All patients will be followed via remote monitoring. The primary end point is time to first episode of AF>6 min detected by the pacemaker. Secondary endpoints include amount of AF, time to stroke, TCI, or thromboembolic event, time to death, quality of life assessments, and a 6-minute walk test.

29. Dansk resume

Syg sinusknude syndrom er årsagen til næsten halvdelen af alle pacemakerimplantationer i Danmark. I løbet af de først 2 år efter implantationen af pacemakere vil halvdelen af disse patienter få konstateret for-kammerflimren. Dette er forbundet med en øget risiko for blodpropper i hjernen og død. Nogle studier tyder på, at der er en øget forekomst af forkammerflimren hos de patienter, hvor pacemakere i en stor andel af tiden stimulerer i forkamrene. DANPACE II er et dansk multicenterstudie med forventet 540 deltagere, der vil undersøge, om det at reducere andelen af pacemakerstimulering i forkamrene vil nedsætte risikoen for at få forkammerflimren.

Protocol amendments

30. Change in study population, May 2017

A recent study has shown that the incidence of AF among pacemaker patients without prior AF is as high in patients with AV block as in patients with SSS (1). It is reasonable to presume that the electromechanical effects of atrial pacing on the myocardium are the same in both populations. Hence, we also assume that they will have the same risk of AF and may therefore also potentially benefit from reduced atrial pacing. Moreover, there is no added risk from participating in this study for patients with AV block compared to patients with SSS. Therefore, we changed the inclusion criteria in the original protocol to include patients with SSS with or without AV block to enable inclusion of patients with AV block, an indication for a DDD pacemaker, and episodes of bradycardia (<60 bpm). Likewise, second- or third-degree AV block was removed from the exclusion criteria.

Minor changes:

- The exclusion criterium 'expected survival <2 years' is changed to 'expected survival <1 year'
- Changes to the investigator list. New investigators from Bisbebjerg Hospital, Hillerød Hospital, and Roskilde Hospital joined the study.
- Additional funding received from The Danish Council for Independent Research (DKK 1.800.000), The Danish Pacemaker and ICD Register (DKK 600.000), and Karen Elise Jensen's Fund (DKK 500.000).

31. Change in sample size estimation, June 2018

After three years of inclusion, approximately 300 patients have been enrolled. Various efforts have been made to increase the rate of enrolment; however, this appears to be futile. Hence, it is no longer realistic to enrol 900 patients into this study as originally protocolled.

1.3. Explanatory endpoints	18
1.4. Subgroups	18
4. Missing data	19
5. Multiplicity considerations	19
6. Sensitivity analyses	19
7. Planned tables	19
8. Planned figures	19
9. Commentary	20

Sample size calculation

We anticipate that 50% of patients in the control group will have developed AF (>6 minutes) within two years, as observed in DANPACE. To show a relative reduction of 25% to an absolute incidence of 37.5% with $\alpha=0.05$ and a $\beta=0.80$, 262 patients must be included in each group. The trial thus included a total of 540 patients.

Randomization

Randomisation is accomplished via a web-based system. Patients are randomised 1:1 to

- DDD-40, or
- DDDR-60

Stratification is performed according to previous AF or atrial flutter (AFL) and sex. In both treatment arms, mode switch is active with a change to DVIR/DDIR/VVIR 60 beats per minute, atrioventricular (AVI) paced 150 milliseconds (ms) and sensed 130 ms with AVI prolongation in case of AVI hysteresis promoting spontaneous conduction up to a maximum AVI of 230 ms, as well as rate-adaptive AVI.

Statistical principles

The primary analysis will be conducted according to the intention-to-treat (ITT) principle (as a superiority analysis) and analysed using a Cox proportional hazard regression model. Kaplan-Meier curves will be used to display differences in AF occurrence over follow-up and compared using a two-sided log-rank test. In addition to analysis of the entire cohort, analyses and Kaplan-Meier curves will be provided for each stratum (+/- previous AF/AFL, PR interval above or below the median, age above or below the median, and in men and women). Predictors for the primary outcome will be assessed using a multivariable Cox proportional hazard regression model. Following baseline covariates will be included in this model: age, sex, bradycardia-tachycardia syndrome, PR interval, LA size, and left ventricular ejection fraction (LVEF) (model 1). The predictive value of individual components of the CHA₂DS₂-VASC score on the primary outcome will be evaluated (model 2). Heterogeneity of treatment effects across levels of different baseline characteristics will be assessed using an interaction term in the Cox proportional hazards model between the treatment group and relevant covariates.

Patients are followed for two years or until death, or study withdrawal. The appropriateness of the proportional hazard (PH) assumption will be assessed using conventional graphical techniques. All estimates will be presented with 95% confidence intervals (CIs) and both relative and absolute risks will be reported. A two-sided P-value ≤ 0.05 will be considered to indicate statistical significance. Secondary analyses are exploratory and results from these will be considered hypothesis-generating.

All statistical analyses will be performed in Stata 17.0.

Outcomes

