Reducing the pacing rate to 40 bpm with the RR function off (DDD-40) significantly reduces the incidence of AF when compared to conventional pacemaker programming at a lower rate of 60 bpm and an activated RR function (DDDR-60) in patients with SSS.

3. Aim

To investigate, in a randomised design, whether reducing the pacing rate to 40 bpm with the rate-response function off reduces the incidence of AF compared to conventional pacemaker programming at a lower pacing rate of 60 bpm and activated rate-response function in patients with SSS.

4. Study design

A Danish, multicentre, randomised study with participation of all Danish pacemaker-implanting centres. Expected inclusion during a period of 2-2½ years, and two years of follow-up.

5. Inclusion criteria

- Sick sinus syndrome with or without AV block and an indication for first-time implantation of a DDD pacemaker: symptomatic sinus pauses (>2 seconds) or bradycardia with or without paroxysmal AF
- Age \geq 18 years
- Patient informed consent

6. Exclusion criteria

- Permanent or persisting (>7 days) AF prior to implantation
- Persistent symptomatic sinus bradycardia and/or chronotropic incompetence where DDD-pacing at a frequency of >40 bpm is indicated (verified with long term ECG monitoring)
- Life expectancy <1 year
- Participation in another interventional research study
- Indication for implantable cardioverter defibrillator (ICD) or cardiac resynchronization therapy (CRT)
- Pregnancy

7. Study course

Patients fulfilling the inclusion criteria will be asked to participate in the study either before the operation or within the first two days after the operation. Randomisation into the two study arms will be internet-based. Randomisation will be stratified for paroxysmal AF and sex documented before pacemaker implantation (bradycardia-tachycardia syndrome). The pacemaker will be programmed into the assigned pacing mode shortly after the implantation, or after randomisation if randomised after implantation. The case report form (CRF) will be internet-based. Patients will be followed-up in the outpatient clinic after 3 months, 12 months, and 24 months. Pacemakers from the following companies may be implanted, as these include home monitoring: Biotronik, Boston Scientific, Medtronic, and St. Jude Medical.

8. Baseline data

- Age
- Sex
- Arrhythmia (SSS with pauses >2 sec without AF/bradycardia-tachycardia syndrome (paroxysmal AF and sinus pauses/bradycardia)/SSS without pauses or AF)

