- Time to first episode of AF >6 hours detected by the pacemaker
- Time to first episode of AF >24 hours detected by the pacemaker
- Number of AF episodes
- Percentage of time in AF
- Time to persistent AF
- Hospitalisation due to AF
- Time to DC cardioversion or medical conversion for AF
- Time to crossover (reprogramming of the pacing rate)
- Time to stroke, TCI, or thromboembolic event
- Time to death
- QOL
- 6MWT

16. Adjudication of endpoints

Primary endpoint: first episode of AF >6 min is adjudicated documented by electrocardiogram. This will be carried out by an independent group of electrophysiologists or competent pacemaker doctors and will be blinded with regard to randomisation arm.

Secondary endpoints: stroke, TCI, thromboembolic events, and first episode of AF >6 hours and 24 hours will be adjudicated by an independent group of electrophysiologists or competent pacemaker doctors and will be blinded with regard to randomisation. Data from patient files will be collected via the study secretariat.

17. Statistics

18. Sample size estimate

Estimation of the study population size: in the control group detection of AF after two years of follow-up is assumed in 50% of the patients as seen in the DANPACE study. With $\alpha=0.05$, $1-\beta=0.80$, and a two-sided test, 262 patients are needed in each group to detect a reduction of an absolute 12.5% (=relative 25 %) to AF in 37.5% of the patients in the intervention group. Therefore, we are planning inclusion of a total of 540 patients randomised equally into the two groups. Patients will be stratified according to prior AF or atrial flutter.

19. Analysis

The incidence of the primary endpoint will be presented with Kaplan-Meier plots, and the statistical comparison between treatment groups will be estimated using log-rank tests and Cox regression

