analysis with calculation of hazard ratios. The following subgroup analyses are planned: effect of the intervention in patients with and without AF prior to pacemaker implantation, effect of the intervention in patients with a baseline PR interval of longer or shorter duration than the median value. The incidence of the secondary endpoints will be presented by Kaplan-Meier plots and compared using log-rank tests, or will be reported as absolute values and percentages, mean value with standard deviation, or median with quartiles, and compared using t-tests provided normally distributed data, or corresponding non-parametric test or χ^2 -test. Multivariate analysis of predictors of the primary endpoint will be done using Cox regression analysis. Besides randomisation we are planning to include in the analysis the following baseline parameters: bradycardia-tachycardia syndrome, age, sex, PR-interval, LA size, LVEF. The predictive value of CHADS₂-VASC-score for the primary endpoint will be evaluated.

20. Side effects, risks, and disadvantages

The implantation implies no additional side effects, risks, complications, or disadvantages compared to standard pacemaker implantation. Potential side effects to the intervention (reduction in pacing rate to 40 bpm) are dizziness, fatigue, and reduced functional capacity. In the event of such symptoms, verified by Holter monitoring and an exercise test to result from a lack of increase in heart rate, the pacemaker may easily be reprogrammed to the conventional setting at 60 bpm. Compared to standard pacemaker follow-up the disadvantages are as follows: slightly prolonged follow-up visits (around 10 minutes longer), and at 12 months follow-up completion of a quality-of-life questionnaire and a 6-MWT.

21. Ethical considerations

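### Randomisation is stratified by prior AF/flutter and sex, but the primary Cox model and log-rank test name no strata; stratifying changes power by about 0 to +6 points under a common treatment effect, with a loss of about 2 possible under interaction

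*Combined protocol and SAP*

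**What the plan says.** On allocation, the SAP (Randomization) states: "Stratification is performed according to previous AF or atrial flutter (AFL) and sex". Protocol section 7 (Study course) has: "Randomisation will be stratified for paroxysmal AF and sex documented before pacemaker implantation (bradycardia-tachycardia syndrome". Protocol section 18 (Sample size estimate) mentions prior AF or flutter and does not name sex.

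On the primary comparison, the SAP (Statistical principles) plans an intention-to-treat analysis "as a superiority analysis) and analysed using a Cox proportional hazard regression model", with Kaplan-Meier curves "compared using a two-sided log-rank test". Protocol section 19 (Analysis) says that "the statistical comparison between treatment groups will be estimated using log-rank tests and Cox regression". None of these sentences names a stratum or a covariate.

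The same or similar factors appear in three other places:
- The SAP gives separate results by level of prior AF/flutter, sex, PR interval and age, and plans interaction terms.
- SAP model 1 is for predictors: "Following baseline covariates will be included in this model: age, sex, bradycardia-tachycardia syndrome", plus PR interval, LA size and LVEF. Treatment is not in its list.
- Protocol section 19 has a similar model that does contain treatment. Its purpose is stated as follows: "Multivariate analysis of predictors of the primary endpoint will be done using Cox regression analysis". The section then sets out what the model holds: "Besides randomisation we are planning to include in the analysis the following baseline parameters: bradycardia-tachycardia syndrome, age, sex, PR-interval, LA size, LVEF".

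**The concern.** Stratified randomisation nearly removes chance imbalance between arms in prior AF. A test that ignores prior AF still allows for that imbalance in its variance. If prior AF predicts the endpoint, the test then spends less than its 5% and gives up some power. Leaving a strong prognostic factor out of a Cox model also pulls the treatment HR towards 1. The plan itself treats prior AF as potentially prognostic: the endpoint is device-detected AF, and prior AF serves as stratum, subgroup factor and (as bradycardia-tachycardia syndrome) candidate predictor.

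The power matters because the June 2018 amendment cut the target from nearly 900 patients to 540 when enrolment fell short. There is also a matter of clarity: the SAP should leave no doubt about which P value is primary if both a stratified and an unstratified one are produced.

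**Working it through.** **Inputs from the documents.** Two-year AF risk 50% v 37.5%, two-sided alpha 0.05, power 0.80, 262 per group, 540 in total, 1:1 allocation, two years of follow-up.

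**Assumed, because the documents do not give them.** Prior-AF HR of 1 to 4; prior-AF prevalence 20-60%; sex not prognostic; censoring 4% a year; permuted blocks of 6; exponential event times; and, unless stated otherwise, one treatment HR common to all strata.

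**The plan's own figure.** The two-proportion formula gives n = [1.96√(2 × 0.4375 × 0.5625) + 0.8416√(0.25 + 0.2344)]² / 0.125² = 246.1. With continuity correction, (246.1/4) × [1 + √(1 + 4/(246.1 × 0.125))]² = 261.8, so 262 per group is reproduced. The implied HR is ln 0.625 / ln 0.5 = 0.678.

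**Calibration.** For prevalence p and prior-AF HR θ, choose the baseline hazard λ and within-stratum treatment HR r so that the marginal risks match the plan:
- control: p·exp(−2λθ) + (1−p)·exp(−2λ) = 0.50
- treated: p·exp(−2λθr) + (1−p)·exp(−2λr) = 0.625

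Example, p = 0.30 and θ = 3: exp(−2λ) = 0.6147, since 0.3 × 0.6147³ + 0.7 × 0.6147 = 0.500. With r = 0.653, 0.6147^0.653 = 0.728, and 0.3 × 0.728³ + 0.7 × 0.728 = 0.625.

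**Tests.** Unstratified Z = (O − E)/√V over all patients. Stratified Z = Σ(O − E)/√ΣV over the four prior AF × sex strata. Reject if |Z| > 1.96. Both tests were applied to the same simulated data.

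**Results, common treatment effect** (8,000 trials per cell, prevalence 20, 30, 45 and 60%, mean 228 events):

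| Prior-AF HR | r | Power, unstratified | Power, stratified | Change (points) | Type I error, unstratified |
|---|---|---|---|---|---|
| 1 | 0.678 | 83.1-83.6% | 82.9-83.4% | −0.1 (mean) | 4.8-5.0% |
| 1.5 | 0.675-0.676 | 83.4-84.3% | 83.6-84.7% | +0.1 to +0.5 | 4.7-5.0% |
| 2 | 0.669-0.671 | 83.6-84.5% | 84.5-85.8% | +1.0 to +1.5 | 3.9-4.7% |
| 3 | 0.653-0.659 | 84.7-86.0% | 87.9-89.6% | +3.0 to +4.0 | 3.4-4.1% |
| 4 | 0.636-0.650 | 86.3-86.8% | 89.8-92.4% | +3.3 to +5.5 | 2.8-3.3% |

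The stratified test's type I error was 4.5-5.3% throughout. As a check on the first row, √(228/4) × 0.3885 − 1.96 = 0.973, which is a power of 83.5%.

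A separate simulation without censoring (20,000 trials per setting, prevalence 30-60%) gave +1.2 to +1.5, +2.8 to +3.8 and +3.4 to +5.6 points at prior-AF HR 2, 3 and 4. Another, at prevalence 30% and 50%, gave unstratified type I error of about 4.4%, 3.6% and 2.9%. Taken together, the rounded ranges are about 0, +0.1 to +0.8, +1 to +2, +3 to +4 and +3 to +6 points at prior-AF HR 1, 1.5, 2, 3 and 4.

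**Results when the treatment effect differs by prior AF** (assumed ratio of treatment HRs 1.5 in either direction; same marginal risks; strata prior AF only; prevalence 30, 45 and 60%; 8,000 trials per cell), change in power in points:

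| Prior-AF HR | Effect weaker in prior AF | Effect stronger in prior AF |
|---|---|---|
| 1.5 | −2.0 to −1.3 | +0.8 to +1.1 |
| 2 | −2.1 to −0.9 | +2.6 to +2.8 |
| 3 | −1.5 to +0.8 | +4.9 to +6.1 |
| 4 | +0.8 to +2.0 | +5.9 to +7.2 |

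**Interval width** (common effect). The model standard error of the log HR is 0.134 unstratified and 0.134-0.135 stratified, so the interval does not narrow. The gain comes from the estimate: the mean HR is 0.68 v 0.67 at prior-AF HR 2, and 0.67 v 0.64-0.65 at prior-AF HR 4. Under the null, the unstratified 95% interval covers 95.4-96.1% at prior-AF HR 2 and 96.7-97.3% at HR 4.

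**The case against.** The strongest objection is that the gain depends on a common treatment effect. The plan itself schedules a prior-AF subgroup analysis and interaction tests, so a differing effect is a live possibility, and the second table shows that stratifying can then cost about 2 points. This stands, and it means the change cannot be called free.

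Second, the design is framed in marginal risks, and an unstratified HR is a legitimate marginal estimand. A stratified HR is conditional on the strata and would sit beside marginal absolute risks. This also stands as a real cost.

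Third, the prior-AF HR and prevalence are not in the documents, and at an HR of 1 to 1.5 there is little or nothing to gain. This limits confidence in the size, not in the omission.

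Fourth, the protocol's predictor model holds treatment, bradycardia-tachycardia syndrome and sex, so an adjusted treatment HR is already planned. It is, but as a predictor analysis and not as the primary comparison, and SAP model 1 does not list treatment. The SAP's per-stratum results are subgroup results: its list includes PR interval and age, which were not randomisation factors.

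Fifth, the SAP is dated 2023 and describes enrolment in the past tense. A change to the primary analysis is sound only if results by arm have not been seen.

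A reader might also infer that the unstratified test is invalid or that the trial is underpowered because of it. The documents support neither. The test errs on the conservative side. In the common-effect runs at the plan's marginal risks, its power stays above 80%. It falls to 75.6-77.8% at prior-AF HR 4 only if the within-stratum HR is held at 0.678, which implies a smaller marginal effect than the one the plan states.

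**Conclusion.** The omission is real: the primary Cox model and log-rank test leave out the factors on which randomisation was stratified, and no other planned analysis takes their place. It is a missed efficiency, not an error of validity. If prior AF is prognostic, the unstratified test is conservative, and under a common treatment effect stratifying recovers from a fraction of a point of power (prior-AF HR 1.5) up to about 6 points (HR 4). If prior AF is not prognostic, nothing is gained. Under an interaction the change can reach about +7 points, or be a loss of about 2 when the effect is weaker in prior AF (HR ratio 1.5) and prior-AF HR is 1.5-2. All sizes assume 540 patients and marginal risks of 50% v 37.5%. Confidence is high for the omission and moderate for the benefit. Making the change is advisable, not essential.

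**What to change.** Add to SAP Statistical principles, in substance: *The primary HR, 95% CI and P value come from a Cox model stratified by previous AF/AFL and sex as recorded in the web randomisation system, with the log-rank test stratified by the same factors. The unstratified Cox model and log-rank test are sensitivity analyses.* State that this HR is conditional on the strata and that the two-year absolute risks by arm remain marginal.

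Align the description of the AF stratum with what the web system used: it is paroxysmal AF in protocol section 7, and AF or flutter in protocol section 18 and the SAP.

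If results by arm have already been seen, keep the written analysis as primary and report the stratified one as a labelled later addition.

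The cost is two or three sentences, the strata option in Stata and retrieval of the stratum values from the web system; no new patient data are needed. The statistical price is a conditional instead of a marginal primary HR and, under the interaction described, up to about 2 points of power.
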